6.3.2 Dose adjustments for QTcF prolongation

If QTcF >500 msec or QTcF prolongation >60 msec from baseline is observed at any point during study treatment, and confirmed, the below guidance must be followed:

1. Assess the quality of the ECG recording and the QT value and repeat if needed
2. Interrupt study treatment until confirmed resolution of QTcF and as per dose reduction guidelines for non-hematological AEs.
3. Determine the serum electrolyte levels (in particular hypokalemia, hypomagnesemia). If abnormal, correct abnormalities before resuming study drug treatment.
4. Review concomitant medication associated with QT prolongation, including drugs with a “Known”, “Possible”, or “Conditional risk of Torsades de Pointes” (refer to www.crediblemeds.org/), and drugs with the potential to increase the risk of study drug exposure related QT prolongation.
5. Check study drug dosing schedule and treatment compliance.

After confirming ECG reading at site, if QTcF > 500 msec

- Interrupt study treatment
- Repeat ECG and confirm ECG diagnosis by a cardiologist or central ECG lab
- If QTcF confirmed > 500 msec:
 - Correct electrolytes, eliminate culprit concomitant treatments, and identify and address clinical conditions that could potentially prolong the QT as per the ECG and QTc Clinical Safety Standards Guidelines Section 3.3.1.
 - Consult with a cardiologist (or qualified specialist)
 - Increase cardiac monitoring as indicated, until the QTcF returns to ≤ 480 msec.
- After resolution to ≤ 480 msec, consider re-introducing treatment at reduced dose, and increase ECG monitoring for the next treatment(s), (e.g. pre-dose and 2 hours post dose after one week and two weeks of treatment re-introduction):

- If QTcF remains ≤ 500 msec after dose reduction, continue planned ECG monitoring during subsequent treatment
- If QTcF > 500 msec recurs after dose reduction, discontinue patient from trial.

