4.1 Description of study design

The study is a phase 3, multi-center, open-label randomized study of oral asciminib versus bosutinib in patients with Chronic Myelogenous Leukemia in chronic phase (CML-CP), previously treated with 2 or more tyrosine kinase inhibitors.

The trial is designed to compare the efficacy and safety of asciminib with that of bosutinib in the treatment of patients with CML-CP having previously been treated with a minimum of two prior ATP-binding site TKIs. Patients intolerant to the most recent TKI therapy must have BCR-ABL1 ratio $> 0.1\%$ IS at screening and patients failing their most recent TKI therapy must meet the definition of treatment failure as per the 2013 ELN guidelines ([Baccarani et al 2013](#)). No more than 66 patients (approximately 30% of the overall trial population) that are intolerant to their most recent TKI therapy with BCR-ABL1 $< 1\%$ will be recruited in order to ensure that the CML third line patient population is adequately represented.

The study will also investigate secondary endpoints for efficacy, safety and PK of single-agent asciminib compared to bosutinib. Tolerability, PK, PRO and exploratory biomarker activities will also be assessed. Safety and efficacy data for patients switching to asciminib will be collected and analyzed separately.

Patients meeting all of the inclusion and none of the exclusion criteria will be randomized into one of the 2 treatment arms, based on a 2:1 randomization between the asciminib arm and the bosutinib arm.

[figure not shown]
The randomization will be stratified to ensure the study population is balanced between the arms with respect to cytogenetic response status (See [Section 7.2.1.2](#)) at screening as follows:

- Major cytogenetic response (complete or partial)
- No major cytogenetic response (minor, minimal or none)

Patients will continue to receive the assigned study treatments (asciminib or bosutinib) until the end of study treatment period as defined in [Section 4.3](#). Patients who discontinue their study treatment at any time during the study will be followed up for survival and for progression to AP/BC for up to 5 years from the date the last randomized patient receives the first dose (irrespective of treatment switch for patients failing bosutinib).

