4.3 Definition of end of study

The patients are treated in the study up to end of study treatment period defined as up to 96 weeks after the last patient receives the first dose or up to 48 weeks after the last patient has switched to asciminib treatment whichever is longer unless patients have discontinued treatment earlier. The end of the study, concluding the survival follow-up, will occur 5 years from the date when the last patient enrolled into the study receives the first dose of the randomized treatment.

The primary analysis (cut-off date) is defined as the date when all randomized patients have been on study treatment for 24 weeks ([Section 10.4](#)) or discontinued earlier. Subsequent to this

analysis, the primary clinical study report (CSR) will be developed. Following the cut-off date for the primary CSR, the study will remain open. Patients who are ongoing at the time of the primary analysis will continue to receive the assigned study treatments (asciminib or bosutinib) during the study treatment period as defined above. The end of study treatment analysis will be conducted with a cut-off date 30 days after the end of study treatment period to ensure all available treatment data from all patients in the study is analyzed and summarized in a CSR.

After the end of the study treatment period the assigned study treatment will be made available to patients who in the opinion of the Investigators are still deriving clinical benefit. This may be outside of this study through alternative options including, but not limited to, an expanded access/compassionate use /managed access program or access to commercial supplies in applicable countries.

Patients will be followed for survival and progression for up to 5 years from the date the last randomized patient receives the first study dose (irrespective of treatment switch for patients failing bosutinib). Information on subsequent treatments will also be collected. An updated analysis of OS and PFS will be performed at the end of the follow-up period in the final study CSR.

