6.3 Dose modifications

6.3.1 Dose modification and dose delay

[figure not shown]
For patients who do not tolerate the protocol-specified dosing schedule, dose interruptions and/or reductions are either recommended or mandated in order to allow the patient to continue the study treatment.

These dose modifications are summarized in [Table 6-2](#). The dose reduction indicated as “recommendations” are provided to assist investigators in the event the patient experiences toxicity. However, deviations from “mandatory” dose interruptions and/or reductions are not allowed and mandatory interruptions or reductions must be strictly followed. Re-escalation to asciminib 40 mg BID is permitted if a change in the patient’s individual benefit/risk assessment at the lower dose level is seen. Re-escalation will be allowed only once for any given patient on the asciminib arm per protocol. Permanent treatment discontinuation is mandatory for specific events indicated as such in [Table 6-2](#). Any dose changes must be recorded on the Dosage Administration Record eCRF.

[figure not shown]
A patient must discontinue treatment with either asciminib or bosutinib if, after treatment is resumed at a lower dose level, the toxicity recurs with the same or worse severity, except for recurrence of cytopenias ([Table 6-2](#)). If a patient requires a dose interruption of > 28 days for each non-hematologic toxicity, then the patient must be discontinued from the study treatment. If a hematologic toxicity (cytopenia Grade 3 or 4) lasts for more than 42 days without recovery to at least a Grade 2, despite TKI interruption and adequate management (including hematopoietic growth factors), then the patient must be discontinued from the study treatment.

Table 6-2 Criteria for dose reduction/interruption and re-initiation of asciminib and bosutinib treatment for adverse drug reactions

[figure not shown]
Dose modifications for both asciminib and bosutinib		
Please note that if a patient requires a dose interruption of > 28 days for each toxicity, then the patient must be discontinued from the study treatment		
Worst toxicity CTCAE Grade 4.03	Asciminib	Bosutinib
Investigations (Hematologic) If a hematologic toxicity (cytopenia Grade 3 or 4) lasts for more than 42 days without recovery to at least a Grade 2, despite TKI interruption and adequate management (including hematopoietic growth factors), then the patient must be discontinued from the study treatment.		
Neutropenia (ANC)		

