> 20.0 x ULN	Mandatory: Hold dose. Repeat LFTs ^b as soon as possible, preferably within 48-72 hours from awareness of the abnormal results; monitor LFTs ^b weekly, or more frequently if clinically indicated, until resolved to ≤ 3 x ULN (or ≤ 5 x ULN for patients with baseline value > 3.0 -5.0 x ULN), then resume treatment at reduce dose ↓ 1 dose level. Only 1 dose reduction is allowed; if reoccurs at > 5 x ULN, discontinue patient from study drug treatment.	Mandatory: Hold dose. Repeat LFTs ^b as soon as possible, preferably within 48-72 hours from awareness of the abnormal results; monitor LFTs ^b weekly, or more frequently if clinically indicated, until resolved to ≤ 2.5 x ULN (then Recommendation: If resolved in ≤ 28 days, reduce dose ↓ 1 dose level maintain dose level Recommendation: If resolved in > 28 days, Discontinue patient from study drug treatment

[figure not shown]
Dose modifications for both asciminib and bosutinib Please note that if a patient requires a dose interruption of > 28 days for each toxicity, then the patient must be discontinued from the study treatment		
Worst toxicity CTCAE Grade 4.03	Asciminib	Bosutinib
Combined ^c elevations of AST or ALT and total bilirubin		
For patients with normal baseline ALT and AST and total bilirubin value: AST or ALT >3.0 x ULN combined with total bilirubin >2.0 x ULN without evidence of cholestasis ^d For patients with elevated baseline AST or ALT or total bilirubin value [AST or ALT >2 x baseline AND > 3.0 x ULN]	Mandatory: Permanently discontinue patient from study drug treatment. Repeat as soon as possible, preferably within 48 hours from awareness of the abnormal results, then with weekly monitoring of LFTs ^b), or more frequently if clinically indicated, until AST, ALT, or bilirubin have resolved to baseline or stabilization over 4 weeks. Refer to Section 6.3.3.1 for additional follow-up evaluations as applicable.	Mandatory: Permanently discontinue patient from study drug treatment. Repeat as soon as possible, preferably within 48 hours from awareness of the abnormal results, then with weekly monitoring of LFTs ^b), or more frequently if clinically indicated, until AST, ALT, or bilirubin have resolved to baseline or stabilization over 4 weeks. Refer to Section 6.3.3.1 for additional follow-up evaluations as applicable.
Investigation (metabolic)		
Asymptomatic amylase and/or lipase elevation		

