Dose modifications for both asciminib and bosutinib		
Please note that if a patient requires a dose interruption of > 28 days for each toxicity, then the patient must be discontinued from the study treatment		
Worst toxicity CTCAE Grade 4.03	Asciminib	Bosutinib

If combined elevations of AST or ALT and total bilirubin do not meet the defined thresholds, please follow the instructions for isolated elevation of total bilirubin and isolated elevation of AST/ALT, and take a conservative action based on the degree of the elevations (e.g. discontinue treatment at the situation when hold dose is needed for one parameter and discontinue treatment is required for another parameter). After all elevations resolve to the defined thresholds that allow treatment re-initiation, re-start the treatment either at the same dose or at one dose lower if meeting a criterion for dose reduction
 
^d “Cholestasis” defined as ALP elevation (>2.0 x ULN and R value <2) in patients without bone metastasis, or elevation of ALP liver fraction in patients with bone metastasis
 
Note: The R value is calculated by dividing the ALT by the ALP, using multiples of the ULN for both values. It denotes whether the relative pattern of ALT and/or ALP elevation is due to cholestatic (R ≤ 2), hepatocellular (R ≥ 5), or mixed (R >2 and < 5) liver injury
 
* Note: If total bilirubin > 3.0 x ULN is due to the indirect (non-conjugated) component only, and hemolysis as the etiology has been ruled out as per institutional guidelines (e.g., review of peripheral blood smear and haptoglobin determination), then ↓ 1 dose level and continue treatment at the discretion of the investigator.
 
** Note: A CT scan or other imaging study to assess the pancreas, liver, and gallbladder must be performed within 1 week of the first occurrence of any ≥ Grade 3 of amylase and/or lipase. If asymptomatic Grade 2 elevations of lipase and/or amylase occur again at the reduced dose, patients will be discontinued permanently from study treatment.
 
*** Note: antidiarrheal medication is recommended at the first sign of abdominal cramping, loose stools or overt diarrhea
		

[figure not shown]

Table 6-3 Dose reduction steps for asciminib and bosutinib

Dose reduction*			
	Starting dose level – 0	Dose level – 1	
Asciminib BID	40 mg tablet BID (total daily dose 80 mg)	20 mg tablet BID (total daily dose 40 mg)	
*Dose reduction should be based on the worst toxicity demonstrated at the last dose.			

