6.3.3 Follow-up for toxicities

Patients whose treatment is permanently discontinued due to a study drug related adverse event or clinically significant laboratory value, must be followed up at least once a week for 4 weeks, until resolution or stabilization of the event, whichever comes first. Appropriate clinical experts such as ophthalmologist, endocrinologist, dermatologist, psychiatrists etc. should be consulted as deemed necessary. All patients must be followed up for adverse events and serious adverse events for 30 days following the last dose of study treatment.

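### Section 6.3.2 takes a patient with recurrent QTcF above 500 msec out of the trial, which read literally is incompatible with the follow-up required in Sections 6.3.3, 4.1 and 4.3

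*Combined protocol and SAP*

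**What the plan says.** All references are to the Amendment 3 protocol unless stated otherwise.

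- **Section 6.3.2** sets out mandatory steps for a confirmed QTcF above 500 msec: interrupt study treatment, correct causes, monitor until QTcF is 480 msec or less, then consider restarting at a reduced dose. Its last step is "If QTcF > 500 msec recurs after dose reduction, discontinue patient from trial".
- **Section 6.3.3** says that patients permanently taken off treatment for a clinically significant laboratory value or a drug-related adverse event "must be followed up at least once a week for 4 weeks, until resolution or stabilization of the event, whichever comes first". It adds: "All patients must be followed up for adverse events and serious adverse events for 30 days following the last dose of study treatment".
- **Section 4.1** says: "Patients who discontinue their study treatment at any time during the study will be followed up for survival and for progression to AP/BC". The limit is 5 years from the last randomized patient's first dose. **Section 4.3** repeats this: "Patients will be followed for survival and progression for up to 5 years".
- **Section 6.3.1** gives the general rule for a toxicity that returns after a dose reduction: "A patient must discontinue treatment with either asciminib or bosutinib if, after treatment is resumed at a lower dose level, the toxicity recurs", with an exception for cytopenias only. Table 6-2 is in line with it. For asciminib patients with AST or ALT above 20 x ULN it says "Only 1 dose reduction is allowed; if reoccurs at > 5 x ULN, discontinue patient from study drug treatment". Its footnote on asymptomatic Grade 2 lipase or amylase elevations says that if these "occur again at the reduced dose, patients will be discontinued permanently from study treatment".

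**The concern.** Section 6.3.2 speaks of study treatment throughout and changes to *trial* only in its final step. In this protocol the two are not interchangeable. The glossary has separate entries for study treatment discontinuation and for stopping study participation, and Section 7.1.2 uses discontinuation from the study for screen failures, who really do leave.

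A site that follows the last step to the letter would stop collecting data on a patient whose QTcF has exceeded 500 msec again after a dose reduction. For that patient, safety data after the event matter most. PFS and OS would also be censored early. Under Section 10.5.2 of the Amendment 1 protocol, a patient without an event is censored for PFS at the last study assessment or post-treatment follow-up, and a living patient is censored for OS at the last contact. The rule applies to both study drugs.

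**Working it through.** The plan states no figure to reproduce. The check sets the instructions side by side and then counts what is left open for one affected patient.

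**Comparison of the text**

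| Requirement | Who is covered | QTcF exception? | Possible after leaving the trial? |
|---|---|---|---|
| 30-day AE/SAE follow-up (6.3.3) | All patients | None | No |
| At least weekly follow-up for 4 weeks, or until resolution or stabilization if sooner (6.3.3) | Permanent stop for a drug-related AE or a clinically significant laboratory value | None | No |
| Survival and AP/BC progression follow-up, up to 5 years (4.1, 4.3) | Section 4.1: anyone who stops study treatment, at any time; Section 4.3: patients generally | None | No |

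The conflict with the 30-day rule does not depend on whether the QTcF event is attributed to the drug. The conflict with the weekly rule does.

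The comparison with Section 6.3.1 and Table 6-2 shows a difference in scope, not a contradiction: those rules stop treatment, while Section 6.3.2 stops trial participation. Section 6.3.2 does not itself say that follow-up ends; that follows only from reading *trial* literally.

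The glossary does not settle the matter. It dates the end of participation at the later of the final evaluation visit and treatment discontinuation, without saying which follow-up survives.

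**Follow-up left open for one affected patient**

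Table 7-1 schedules survival contacts every 12 weeks (84 days). Five years is 1,826 days, and 1,826 / 84 = 21.7 intervals. For the last randomized patient, the number of contacts after treatment stops at week *w* is the whole part of (1,826 − 7*w*) / 84. The protocol gives no stop times, so three are assumed:

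| Assumed stop | Calculation | Contacts |
|---|---|---|
| Week 4 | (1,826 − 28) / 84 = 21.4 | 21 |
| Week 24 | (1,826 − 168) / 84 = 19.7 | 19 |
| Week 96 | (1,826 − 672) / 84 = 13.7 | 13 |

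Patients randomized earlier have more contacts at stake, because the 5 years run from the last randomized patient's first dose. The 30-day follow-up and, where it applies, the weekly follow-up come on top.

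**How many patients**

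The documents give no rate of recurrence after dose reduction, so no count can be projected. As context only, Section 1.2.1.2 reports no QT prolongation at asciminib 40 mg BID in Phase I, and two new values above 500 msec across all asciminib monotherapy, one at 80 mg QD and one at 120 mg QD. Neither is reported as a recurrence after dose reduction.

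**Primary endpoint**

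Under Section 10.4.3 of the Amendment 1 protocol, stopping randomized treatment before week 24 for any reason counts as non-response. The classification is the same whether the patient leaves treatment or leaves the trial.

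**The case against.** The best counter-argument is that the protocol already resolves this. A patient stopped for QTcF has necessarily stopped study treatment, so Section 4.1 applies by its own terms, and the section immediately after 6.3.2 imposes 30-day follow-up on everyone. The Amendment 1 change log states the design rule for Section 7.1.6: everyone is followed for survival except patients who died, withdrew consent or were lost. It also records a clarification separating stopping treatment from stopping the study. The glossary links the end of data collection to the patient's own withdrawal of consent. Section 7.1.6 of the Amendment 1 protocol even calls for an end-of-study visit for patients who then enter survival follow-up, so loose study-exit wording is not new here. Finally, the Amendment 3 text of Sections 7.1.6 and 7.1.7 is not in the material available, and it may say what discontinuation entails.

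Most of this stands as evidence of intent: a treatment stop is almost certainly what was meant. It does not remove the conflict. Two mandatory instructions remain, nothing visible says which prevails, and the site has to choose. That the sponsor took care in Amendment 1 to separate the two kinds of discontinuation is a reason to keep the wording exact. Section 6.3.2 of the Amendment 1 protocol lacks this sentence, and the later change logs describe only QT-drug classification and web-reference changes for the section, so the wording looks inadvertent. The objection is also right that the weekly toxicity follow-up applies only if the QTcF event is judged a drug-related adverse event, and that the contact counts assume every survival contact is lost.

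**Conclusion.** The point holds. Read literally, the last step of Section 6.3.2 cannot be carried out together with Sections 6.3.3, 4.1 and 4.3. It is a minor wording error in an operative safety rule. Very few patients would be affected, possibly none, and the week-24 MMR endpoint would not change. For an affected patient, 30 days of AE/SAE follow-up and a long run of 12-weekly survival contacts are left open: 21, 19 or 13 for the last randomized patient under the assumed stop times.

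The conclusion rests on the literal reading of *trial* and on there being no overriding statement in the Amendment 3 Sections 7.1.6 and 7.1.7, which could not be checked. The Amendment 1 version of 7.1.6 excludes only death, loss to follow-up and withdrawal of consent from survival follow-up.

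**What to change.** In Section 6.3.2, replace the instruction to remove the patient from the trial with: *permanently discontinue study treatment; continue follow-up per Sections 6.3.3, 4.1, 4.3 and 7.1.6*. Leave the QTcF threshold and the dose-reduction rule as they are.

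The cost is one phrase in the protocol. No visits are added beyond those already required of patients who stop treatment.

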6.3.3 Follow-up for toxicities

Patients whose treatment is permanently discontinued due to a study drug related adverse event or clinically significant laboratory value, must be followed up at least once a week for 4 weeks, until resolution or stabilization of the event, whichever comes first. Appropriate clinical experts such as ophthalmologist, endocrinologist, dermatologist, psychiatrists etc. should be consulted as deemed necessary. All patients must be followed up for adverse events and serious adverse events for 30 days following the last dose of study treatment.

6.3.3.1 Follow up on potential drug-induced liver injury (DILI) cases

Patients with transaminase increase combined with TBIL increase may be indicative of potential DILI, and should be considered as clinically important events.

The threshold for potential DILI may depend on the patient's baseline AST/ALT and TBIL value; patients meeting any of the following criteria will require further follow-up as outlined below:

- For patients with normal ALT and AST and TBIL value at baseline: AST or ALT > 3.0 x ULN combined with TBIL > 2.0 x ULN
- For patients with elevated AST or ALT or TBIL value at baseline: [AST or ALT > 2 x baseline AND > 3.0 x ULN] OR [AST or ALT > 8.0 x ULN], combined with [TBIL > 2 x baseline AND > 2.0 x ULN]

Medical review needs to ensure that liver test elevations are not caused by cholestasis, defined as ALP elevation > 2.0 x ULN with R value < 2 in patients without bone metastasis, or elevation of ALP liver fraction in patients with bone metastasis.

Note: (The R value is calculated by dividing the ALT by the ALP, using multiples of the ULN for both values. It denotes whether the relative pattern of ALT and/or ALP elevation is due to cholestatic ($R \leq 2$), hepatocellular ($R \geq 5$), or mixed ($R > 2$ and < 5) liver injury).

In the absence of cholestasis, these patients should be immediately discontinued from study drug treatment, and repeat LFT testing as soon as possible, preferably within 48 hours from the awareness of the abnormal results. The evaluation should include laboratory tests, detailed history, physical assessment and the possibility of liver metastasis or new liver lesions, obstructions/compressions, etc.

1. Laboratory tests should include ALT, AST, albumin, creatinine kinase, total bilirubin, direct and indirect bilirubin, GGT, prothrombin time (PT)/INR and alkaline phosphatase.
2. A detailed history, including relevant information, such as review of ethanol, concomitant medications, herbal remedies, supplement consumption, history of any pre-existing liver conditions or risk factors, should be collected.
3. Further testing for acute hepatitis A, B, C or E infection and liver imaging (e.g. biliary tract) may be warranted.

4. Obtain PK sample, as close as possible to last dose of study drug, if PK analysis is performed in the study.
5. Additional testing for other hepatotropic viral infection (CMV, EBV or HSV), autoimmune hepatitis or liver biopsy may be considered as clinically indicated or after consultation with specialist/hepatologist.

All cases confirmed on repeat testing meeting the laboratory criteria defined above, with no other alternative cause for LFT abnormalities identified should be considered as “medically significant”, thus, met the definition of SAE ([Section 8.2.1](#)) and reported as SAE using the term “potential drug-induced liver injury”. All events should be followed up with the outcome clearly documented.

